**Subject with any of the following eligibility criteria IPDs will be removed from the Efficacy Analysis Set:**

- **Subject does not have histologically proven stage IIIB, IIIC, or IVM1a melanoma eligible for complete surgical resection**
- **Subject is not a candidate for intralesional therapy**

**For purposes of the Efficacy Analysis Set sensitivity analysis, subjects who did not receive the assigned treatment arm will be excluded from the analysis.**

The **Efficacy Analysis Set** will be used for a sensitivity analysis of the **primary** efficacy endpoint.

## 7.4 Subgroup Analyses

Efficacy analyses will be conducted utilizing the subgroups as defined in [Section 4.2](#).

**Safety analyses will be conducted on the following subgroups: age group (< 65, ≥ 65 and < 75, ≥ 75), sex, and race (white vs not white).**

## 8. Planned Analyses

### 8.1 Interim Analysis and Early Stopping Rules

Two interim analyses with no formal stopping rules are planned to evaluate safety when approximately 40 and 75 subjects randomized to talimogene laherparepvec have had the opportunity to complete the safety follow-up visit. **The database will be cleaned**

**and a database snapshot will be used in each analysis.** A Data Review Team (DRT) independent of the talimogene laherparepvec product team will review the first interim analysis (see [Section 8.1.1](#)). The DRT will also review some efficacy endpoints (eg, R0 resection rate, pCR rate, response to neoadjuvant treatment).

The **Amgen study** team will review the second interim analysis because it will occur after all subjects have been already treated, have completed safety follow-up, and no additional interventions that may influence safety or efficacy of the investigational product are planned after this time point. The **Amgen study** team will also review some efficacy endpoints (eg, R0 resection rate, pCR rate, response to neoadjuvant treatment).

An additional third interim analysis with no formal stopping rule is planned to evaluate RFS approximately 1 year after the end of randomization. This analysis will be conducted by the Amgen study team. **The database will be cleaned and a locked database will be used for this analysis.**

Ad hoc analyses for safety or some efficacy endpoints (eg, response to neoadjuvant treatment, R0 resection rate, pCR rate) may be conducted before the planned primary and/or final analyses if interim data are required for submission to regulatory authorities. These ad hoc analyses will be executed by the **Amgen** study team.

#### **8.1.1 Data Review Team (DRT)**

A Data Review Team (DRT) independent of the talimogene laherparepvec product team will be formed. The DRT will consist of one Amgen biostatistician and two Amgen clinicians (one from Clinical Development and one from Global Safety) who collectively have experience in oncology clinical research and in the conduct and monitoring of randomized clinical trials. In addition, the DRT will include one external clinical expert (eg, a surgical oncologist in melanoma) not directly involved in the conduct of the study. The DRT will be supported by a statistician internal to Amgen but independent of the talimogene laherparepvec product team. This DRT will review unblinded safety data at the first interim analyses. This independent DRT will be governed by a study-specific DRT charter.

#### **8.2 Primary Analysis**

**The primary analysis for RFS will occur at the later time of either the occurrence of approximately 64 events (local, regional, or distant recurrence of melanoma or death) or approximately 2 year after the end of the randomization. The database will be cleaned and a locked database will be used in the analysis.**

### **8.3 Final Analysis**

The final analysis will occur approximately 5 year after the end of randomization. The database will be cleaned and a locked database will be used in analysis.

### **8.4 Additional Analysis**

An additional analysis will also occur approximately 3 years after the end of randomization. The database will be cleaned and a locked database will be used in analysis.

## **9. Data Screening and Acceptance**

### **9.1 General Principles**

The objective of the data screening is to assess the quantity, quality and statistical characteristics of the data relative to the requirements of the planned analyses.

### **9.2 Data Handling and Electronic Transfer of Data**

Amgen's Clinical Data Management department will provide all data to be used in the planned analyses. This study will use the RAVE database. Antibody will be processed by vendor for Amgen BSM and then transferred to Amgen's Medidata Rave database to be accessed for analysis.

### **9.3 Handling of Missing and Incomplete Data**

#### **9.3.1 Efficacy**

The method for handling missing data is described in the definition for each of the efficacy endpoints ([Section 4](#)).

#### **9.3.2 Safety**

Partial or missing dates of adverse events and concomitant medications will be imputed.

### **9.4 Detection of Bias**

#### **9.4.1 Important Protocol Deviations (IPD) Impact**

All IPDs will be reported, documented, and stored in eClinical (Clinical Trial Management System). An IPD report will be produced using Cognos by the Clinical Study Manager for regularly scheduled Study Team IPD Review meetings and before each analysis.

Lack of protocol compliance and the potential for biased statistical analyses will be examined by tabulating subjects with important protocol violations by study arm. A

listing of all IPDs will also be provided. High rates of lack of compliance or differing rates between study arms could be an indication of bias. A sensitivity analysis will be performed on the primary efficacy endpoint for the impact of important protocol deviations by repetition of analysis using the **Efficacy Analysis Set** (see [Section 7.3](#)).

#### **9.4.2 Timing Bias Impact**

Differences between the arms in the Schedule of Assessments (SOA) may result in a possible bias in the detection of overall recurrence (local, regional, or distant recurrence).

If 10% or more of the overall post-surgery recurrences (both arms combined), regardless of surgical outcome, occur within the first 6 months post-surgery, then a stratified piece-wise Cox model will be used to allow estimation of within interval treatment hazard ratios of talimogene laherparepvec plus surgery compared to surgery alone adjusting for the randomization factors for the overall ITT population (Collett 2003). The time intervals are defined as:  $\leq 6$  months post-surgery, then every 6 months thereafter. Please see [Appendix B](#) for code fragments.

#### **9.4.3 Subsequent Anti-Cancer Therapy Impact**

To evaluate the potential bias introduced by the use of subsequent anti-cancer therapy on RFS, **three separate sensitivity analyses will be performed based on the type of anti-cancer therapy received: (a) any subsequent anti-cancer therapy, (b) adjuvant anti-cancer therapy for melanoma, (c) non-adjuvant anti-cancer therapy for melanoma. For analyses (a) and (b), subjects who receive the respective subsequent anti-cancer therapy type prior to an RFS event will be censored at the last evaluable tumor assessment prior to receiving the respective subsequent anti-cancer therapy type. For analysis (c), subjects who receive non-adjuvant anti-cancer therapy for melanoma prior to an RFS event will be an event at the last evaluable tumor assessment prior to receiving the non-adjuvant anti-cancer therapy for melanoma.**

**These sensitivity analyses will be repeated using the alternative definition for RFS as defined in RFS Sensitivity #1 ([Section 4.1.1](#)).**

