Informed Consent	X				
Review of Medical/Surgical History	X				
Demographic Data (sex, age or date of birth, race, and ethnicity)	X				
Review of Eligibility Criteria	X				
Concomitant Medications	X		X	X	
Adverse and Serious Adverse Events	X		X	X	
Physical Exam	X			X	
Vital Signs	X		X	X	
ECOG Performance Status	X			X	
Surgical Safety Evaluation (including wound closure, drain time, and post operation infection)				X	
Subsequent Anticancer Therapy for Melanoma				X	X
Survival					X
LOCAL LABORATORY ASSESSMENTS					
Urine or Serum Pregnancy Test		X		X	
Hematology	X			X	
Chemistry	X			X	
Serum LDH	X				
PT, PTT or aPTT, INR	X				

Footnotes defined on next page of the table

Table 3. Schedule of Assessment for Arm 2 (Surgery Alone)

	Screening ^a		Treatment Period ^b	Follow-up Period ^c	
	≤ 28 days	≤ 3 days	At time of Surgery (Week 1 to 6)	Safety Follow-up 30 (+15) days	Long-term Follow-up Every 3 months (± 30 days) for 3 years then every 6 months (± 30 days) until 5 years after randomization
CENTRAL LABORATORY ASSESSMENTS					
Archived Tumor Tissue for Biomarker Analyses			Submit to central laboratory within 28 days after randomization		
Archived Tumor Tissue for BRAF ^{V600} Mutation Testing			Submit to central laboratory within 28 days after randomization if BRAF ^{V600} mutation status is unknown prior to screening and was not tested at local laboratory		
Tumor Biopsy			X		
Blood for Biomarker Development			X		
TREATMENT					
Surgery			X		
RADIOGRAPHIC IMAGING, CLINICAL, AND HISTOLOGICAL TUMOR ASSESSMENTS					
Radiographic Imaging (CT, PET/CT, MRI)	X				X
Clinical Tumor Measurement and Response Assessment	X				X
Histological Tumor Assessment of Surgical Specimen ^d			X		

Page 2 of 2

^a For additional information regarding the procedures performed during screening procedures and the timing of the procedures please refer to [Section 7.2.1](#).

^b For additional information regarding the procedures performed during treatment and the timing of the procedures please refer to [Section 7.2.2](#).

^c For additional information regarding the procedures performed during safety follow-up and long-term follow-up and timing of the procedures please refer to [Section 7.2.3](#) and [Section 7.2.4](#), respectively.

^d Surgical specimens will be assessed for presence of viable tumor and tumor margin status for cutaneous and subcutaneous tumor; please refer to [Section 7.2.2](#).

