7.2.4 Long-term Follow-up

All randomized subjects will be contacted by telephone, or clinic visit, to assess survival status, collect adverse events deemed by the investigator to be potentially related to talimogene laherparepvec (Arm 1 only), and, if applicable, commencement of any subsequent anticancer melanoma therapy. Follow-up will occur every 3 months (± 30 days) for 3 years following the safety follow-up visit and then every 6 months (± 30 days) until death, subject withdraws full consent, or up to 5 years after the last subject is randomized, which is first.

Radiographic tumor imaging, clinical tumor assessments, and tumor response assessments, will be performed as documented in [Section 7.2.2](#) every 3 months (± 30 days) for 3 years following the safety follow-up visit and then every 6 months (± 30 days) until distant disease recurrence, death, subject withdraws full consent, or up to 5 years after the last subject is randomized, whichever is first. Local and regional recurrences will be reported until appearance of distant recurrence, or end of study, whichever is first. Local recurrence is defined as histologically or cytologically confirmed reappearance of melanoma in the area of up to 2 cm from the scar from the surgical

excision or at the edge of the skin graft if that was used for closure. Regional recurrence (excludes local recurrence) is defined as histologically, cytologically, or radiographically confirmed reappearance of melanoma in the regional lymph node basin. New in-transit melanoma metastases in the regional lymphatic drainage will be reported as regional recurrence. Histological or cytological confirmation of new in-transit metastases is recommended but is not required. Distant metastases exclude local and regional recurrence and will include distant cutaneous/subcutaneous metastases, distant nodal metastases, or visceral, central nervous system, brain, or bone metastases.

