When an non-index lesion splits into two or more lesions, the apparently larger lesion will be reported as a non-index lesion. All other smaller lesions will be reported as new non-index lesions with an indication that the lesion split from the specified lesion. In this case, appearance of a new lesion from a previous lesion that split will not be considered

disease progression solely due to appearance of a new lesion (may be considered disease progression due to > 25% increase in the sum of the products of the perpendicular diameters of all index tumors since baseline, or the unequivocal appearance of a new tumor, other than the product of the split tumor, since the last response assessment time point).

Measureable Tumor Assessment/Burden:

Baseline Documentation of “Index Lesions”:

All baseline evaluations should be performed as close as possible to randomization and never more than 4 weeks (ie, 28 days) prior to randomization.

At baseline, up to 10 measurable cutaneous, nodal, or soft tissue lesions will be chosen to measure over the course of therapy. The distribution of these index lesions should be representative of the subject’s overall disease status. Index lesions should be selected on the basis of their size (lesions with longest bi-dimensionally perpendicular diameters) and suitability for accurate repeated measurements by imaging techniques (CT, MRI or ultrasound) and/or other method such as clinical exam.

The sum of the products of the largest perpendicular diameters of all index lesions will be calculated and reported.

If a subject has multiple small superficial cutaneous melanoma lesions at baseline (each lesions is less than 10 mm in at least 2 dimensions) which in aggregate have a total diameter of ≥ 10 mm in at least 2 dimensions, up to 10 largest lesions that were included in this measurement will be reported as “Index Lesions”, and the sum of the products of the two largest perpendicular diameters of these lesions will be calculated and reported for tumor response assessments.

Baseline Documentation of “Nonindex Lesions”:

All other lesions (or sites of disease), including any measurable lesions that were not chosen as index lesions will be identified as nonindex lesions. Nonindex lesions should be recorded and assessed qualitatively over the course of therapy.

Follow-up “Index Lesions”:

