#### 4. Study Endpoints and Covariates

##### 4.1 Study Endpoints

##### 4.1.1 Primary Endpoint

Recurrence-Free Survival (RFS): The event for RFS is defined as the first of local, regional, or distant recurrence of melanoma or death due to any cause. RFS is defined as time from randomization to the date of the event. The following **four** rules will be used:

1. For subjects having not experienced an event by the cutoff date, RFS will be censored at the last valid tumor evaluation (refer to Section 6 for the definition of last valid tumor evaluation).
2. Subjects who are not confirmed to be disease-free post-surgery (i.e., who do not have an R0 surgical outcome) will be considered to have an event at randomization for RFS.
3. Subjects who withdraw prior to surgery will be considered to have an event at randomization for RFS.
4. Subjects with a non-melanoma tumor or a second malignancy identified before or at surgery will be censored at the day after randomization.

Alternative RFS definitions will be evaluated in sensitivity analyses as follows.

- **RFS Sensitivity # 1: RFS is defined as the first of local, regional, or distant recurrence of melanoma or death due to any cause, regardless of surgical outcome, achieved by omitting rule 2.**

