**Table 2. Study Design Characteristics Example Endpoint Summary Table**

Endpoint	Primary Summary and Analysis Method	Sensitivity Analysis
Primary Endpoint		

 
• RFS
 
	
 
• Log-rank test and 80% CI for the treatment hazard ratio from a proportional hazards model without stratification in the ITT analysis set.
 
• Kaplan-Meier (K-M) estimation by randomized treatment arm.
 
• Simultaneous 80% confidence band for each arm KM estimate from 1 to 5 years per equal-precision band method.
 
• 80% CI for K-M quartiles by arm (where estimable) per Brookmeyer & Crowley.
 
• 80% CI for between-arm quartile difference in KM estimate via bootstrap.
 
	
 
• Repeat with stratification by the two randomization factors
 
• If 10% or more of the overall recurrence (both arms combined) occur within the first 6 months post-surgery, the stratified analysis will be repeated with stratified piece-wise Cox model to estimate within interval hazard ratios adjusting for randomization factors.
 
• Estimate the Cox model hazard ratio with Robins IPCW weighting censoring RFS at the start of all or selected adjuvant therapy for melanoma.
 
• If warranted (eg, the planned adjuvant therapy stratification factor is discordant with the actual for > 10% of all subjects), the stratified analysis will be repeated replacing planned adjuvant therapy with actual adjuvant therapy and/or adjuvant therapy containing selected types of systemic therapy, including immunotherapy.
 
• Cox model and KM analysis of RFS according to randomized treatment and actual adjuvant systemic therapy (yes vs no) with 3 comparisons: all subjects, those with adjuvant systemic therapy, and those without adjuvant systemic therapy.
 
• Repeat with and/or without stratification by the two randomization factors in the efficacy analysis set, if necessary.
 
• Univariate and multivariate proportional hazards models without stratification may be used to explore the prognostic and/or predictive value of baseline covariates using primary endpoint definition and alternative endpoint definition #1 in Section 4.1.1.
 
• Subgroup analyses will be evaluated with a log-rank test and corresponding proportional hazard model without stratification using primary endpoint definition and alternative endpoint definition #1 in Section 4.1.1.
 
• Repeat subgroup analyses with a log-rank test and proportional hazards model with stratification by two randomization factors.
 
• Repeat using sensitivity analysis alternative endpoint definitions (see Section 4.1.1).
 
• Repeat based on the type of anti-cancer therapy received: any subsequent anti-cancer therapy, adjuvant anti-cancer therapy for melanoma, non-adjuvant anti-cancer therapy for melanoma using primary endpoint definition and alternative definition # 1 in Section 4.1.1. Subjects who receive the respective subsequent anti-cancer therapy type prior to an RFS event will be censored at the last evaluable tumor assessment prior to receiving the respective subsequent anti-cancer therapy type.
 

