### 10.5.1 Analyses of Primary Efficacy Endpoint(s)

An overall between-group difference in RFS will be evaluated with a log-rank test and corresponding proportional hazards model without stratification. Sensitivity analyses, using alternate definitions of RFS as defined in [section 4.1.1](#), will be evaluated in the same manner. Additionally, for RFS, a log-rank test and proportional hazards model with stratification by the two randomization factors will also be conducted.

A sensitivity analysis will be performed censoring RFS at the start of all or selected actual adjuvant therapy for melanoma. However, censoring at start of all or selected adjuvant therapy for melanoma may introduce dependent censoring as the ability to receive further adjuvant therapy will likely be correlated with RFS. An inverse probability censoring weighting (IPCW) method (Robins, et al) which may reduce the potential bias will also be used to obtain an estimate of the treatment effect on RFS and may include baseline covariates in [Section 4.2](#).

In order to assess the impact of imbalances in the type of adjuvant therapy, a **stratified** Cox model will be repeated stratifying actual adjuvant systemic therapy (yes vs no). A KM time to event plot for RFS will be generated by 4 groups (Arm 1 with adjuvant systemic therapy, Arm 1 without adjuvant systemic therapy, Arm 2 with adjuvant systemic therapy, Arm 2 without adjuvant systemic therapy), and 2 separate KM plots will be generated by randomized treatment group in subjects with and without adjuvant systemic therapy respectively. If warranted due to actual adjuvant therapy (eg, the planned adjuvant therapy stratification factor is discordant with the actual for > 10% of all subjects), the stratified Cox model analysis will be repeated stratifying on **actual** adjuvant therapy type (**adjuvant systemic therapy with or without radiotherapy vs radiotherapy without adjuvant systemic therapy vs none**).

**To explore the prognostic and/or predictive value of the covariates listed in [Section 4.2](#), univariate and multivariate proportional hazards models without stratification will be used. Subgroup analyses will be evaluated with a log-rank test and corresponding proportional hazards model without stratification.**

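### SAP 9.4.3 censors at the last tumor assessment before therapy, which for early starters is at or before randomization (or undefined) in Arm 2 and about week 12 in Arm 1

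*SAP*

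**What the plan says.** SAP 9.4.3 plans three sensitivity analyses of RFS by type of later therapy. In (a) any subsequent therapy and (b) adjuvant therapy, a subject who receives it before an RFS event "will be censored at the last evaluable tumor assessment prior to receiving the respective subsequent anti-cancer therapy type". SAP Table 2 repeats the rule: such subjects are "censored at the last evaluable tumor assessment prior to receiving the respective subsequent anti-cancer therapy type". Neither place defines the assessment, sets an earliest permitted date, or says what to do when nothing was assessed after randomization.

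The clock is fixed in SAP 4.1.1: "RFS is defined as time from randomization to the date of the event". The same section makes a subject without an R0 outcome an event at randomization.

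The schedules differ by arm:

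- **Baseline, both arms.** Protocol Appendix D wants baseline evaluations close to randomization and "never more than 4 weeks (ie, 28 days) prior to randomization".
- **Arm 2.** In Protocol Table 3, imaging and the row "Clinical Tumor Measurement and Response Assessment" are marked only at screening and in long-term follow-up. Histology of the specimen is marked at surgery.
- **Arm 1.** Protocol 7.2.2 adds imaging, clinical measurement and response assessment at week 12 (± 2 weeks), or shortly before surgery if injections stop early.
- **Safety visit, both arms.** Protocol 7.2.3 lists no tumor assessment, but does record subsequent anticancer therapy.
- **Long-term follow-up.** Protocol 7.2.4: "Follow-up will occur every 3 months (± 30 days) for 3 years following the safety follow-up visit". Imaging and clinical tumor assessment follow the same timetable.

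SAP 10.5.1 handles adjuvant therapy with a different date: "A sensitivity analysis will be performed censoring RFS at the start of all or selected actual adjuvant therapy for melanoma".

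**The concern.** The rule reads the same for both arms, but the schedules make it act differently. Someone who starts adjuvant therapy before the first follow-up scan has no scheduled post-surgery imaging or response assessment, so the rule looks back to the last assessment before surgery. In Arm 1 that is about week 12. In Arm 2 it is screening, which precedes the RFS time origin, or nothing at all if screening does not qualify.

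The analyst must then improvise a choice that affects one arm, in an open-label trial. If negative times fall out, Arm 2 loses event-free, R0-resected subjects and keeps its failures imputed at randomization, while Arm 1 loses nobody this way. The resulting error favors Arm 1, in a section of the SAP meant to detect bias. SAP 9.4.2 recognises that the arms' schedules differ, but only for detecting recurrence, not for this censoring rule.

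**Working it through.** **1. Design inputs.** The plan gives no figure for this sensitivity analysis, so I first reproduced the first row of SAP Table 1, whose inputs the simulation uses.

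- HR = ln 0.70 / ln 0.60 = 0.698 (stated 0.70).
- 80% CI = 0.698 × exp(± 1.2816 × 2/√64) = 0.507 to 0.962 (stated 0.51 to 0.96).
- Probability that the CI lies below 1 = Φ(|ln 0.698| × √64/2 − 1.2816) = 0.562 (stated 0.56).
- Expected events with 18 months' accrual, 2 further years and 10% drop-out over 3.5 years: 64.1 (stated 64).

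**2. Timeline**, with 3 months taken as 91 days, so ± 30 gives 61 to 121.

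- First follow-up scan after surgery: 30 + 61 = 91 to 45 + 121 = 166 days; nominal 30 + 91 = 121.
- From randomization in Arm 2 (surgery days 1-42): 1 + 91 = day 92 to 42 + 166 = day 208.
- From randomization in Arm 1 (surgery days 85-126): 85 + 91 = day 176 to 126 + 166 = day 292.
- Arm 1 week 12, day 1: 11 × 7 + 1 = day 78; ± 14 gives days 64 to 92.

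Anyone starting therapy within 13 weeks (91 days) of surgery therefore starts before the first follow-up scan. If screening counts as the last assessment, the rule gives day −28 to 0 in Arm 2 and about day 64 to 92 in Arm 1.

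**3. Mechanism, one example.** Take 75 per arm, 20% non-R0 and 40% uptake. Each arm has 0.20 × 75 = 15 events at time 0. Of the 60 R0 subjects in Arm 2, 0.40 × 60 = 24 receive adjuvant therapy, and about 23 of them reach its start event-free. If those 23 are dropped, the time-0 failure share is 15/52 = 29% in Arm 2 and 15/75 = 20% in Arm 1, although the arms are identical.

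**4. Simulation with true HR = 1.** 75 per arm, 2-year RFS 0.60 in both arms apart from the time-0 events, Cox model with Efron ties. Assumed, because the documents do not give them: non-R0 rate, adjuvant uptake (both equal across arms) and start 4-12 weeks after surgery, which puts every start before the first scan. Negative times are dropped; events at time 0 stay. Mean HR from two sets of runs (300 / 400 trials per cell; single values are from the 400-trial set):

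| Non-R0 | 20% uptake | 40% uptake | 60% uptake |
|---|---|---|---|
| 0% | 0.99 | 0.99 | 0.96 |
| 10% | 0.96 / 0.94 | 0.86 / 0.88 | 0.74 / 0.77 |
| 20% | 0.95 / 0.93 | 0.80 / 0.82 | 0.67 / 0.69 |
| 30% | 0.91 | 0.80 | 0.64 |

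Monte Carlo error is about ± 0.015 on the log HR. Across the 400-trial cells the 80% CI lay wholly below 1 in 11% to 67% of trials, against a nominal 10%.

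Alternatives in the same setting:

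- Dates floored at randomization: HR 0.95 to 1.00, with zero follow-up from the affected Arm 2 subjects.
- Censoring at the start of therapy: HR 0.99 to 1.01, with the 80% CI below 1 in 8% to 12% of trials.

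**The case against.** **Arm 2 does have an assessment at surgery.** Table 3 marks specimen histology there. If that counted, censoring would fall at surgery in both arms and never before randomization. So a reader should not infer that Arm 2 has no tumor assessment of any kind in this interval. But the nearest SAP definition, the last valid tumor evaluation in Section 6, is a response of CR, PR, SD or PD, which histology is not.

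**The pre-randomization date is an interpretation.** True. Under that same Section 6 definition a screening scan carries no response, so the Arm 2 subject has no censoring date rather than a negative one. Neither reading gives a usable date.

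**The bias needs an unstated implementation.** Also true. The SAP does not say that negative times are dropped. RFS Sensitivity #2 already uses the later of the last evaluation and randomization, and with that floor the bias largely goes. If time-0 events were dropped as well, only R0 subjects would remain, which is in effect the 0% row.

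**There are safeguards.** SAP 9.4.3 repeats these analyses under RFS Sensitivity #1, which removes the non-R0 imputation that drives most of the bias, so the distortion should shrink there. SAP 10.5.1 also censors at start of therapy, adds inverse probability of censoring weighting, and examines actual adjuvant therapy. All analyses are descriptive.

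These points limit the size and seriousness of the problem. The stated rule still dates comparable subjects differently by arm.

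**Conclusion.** The point holds as a should-fix. For subjects who start therapy before the first follow-up scan, the rule in SAP 9.4.3 (a) and (b) and the Table 2 row gives a date at or before randomization, or none, in Arm 2 and about week 12 in Arm 1. This follows from the schedules alone.

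The size is conditional. With negative times dropped, 10-20% non-R0, 20-60% uptake and starts 4-12 weeks after surgery, a true HR of 1 averages roughly 0.96 down to 0.67. If every resection is R0 it is 0.96-0.99. With a floor at randomization it is 0.95-1.00, at the cost of all follow-up from these Arm 2 subjects.

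Three stronger readings are not supported:

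- That all treated Arm 2 subjects are censored before randomization. Those who start after the first scan are censored at a post-surgery scan in both arms, and the SAP's definition of adjuvant therapy gives no start window, so the share affected is unknown.
- That the analysis must show a false benefit for Arm 1. That needs both dropped negative times and a material non-R0 rate.
- That the main result is compromised. Primary RFS and the 10.5.1 analyses do not use this rule.

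**What to change.** In SAP 9.4.3 (a) and (b) and the matching Table 2 row, censor at the date the therapy starts in both arms, consistent with 10.5.1. No floor at R0 surgery is needed: adjuvant therapy follows surgery by definition, and such a floor is undefined for non-R0 subjects, who matter in the Sensitivity #1 repeat.

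The Table 2 row also covers type (c), for which it censors while 9.4.3 imputes an event. Separate (c) when editing the row and reconcile the two.

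The cost is about one SAP sentence and the matching table text, with no new data. The downside is that analysis (b) then largely overlaps the unweighted 10.5.1 analysis.

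If the last-assessment rule is kept as well, define the term and use the later of that assessment and randomization, as RFS Sensitivity #2 does. Report how many subjects per arm are censored at time 0, because they contribute no follow-up.
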